### 7.1.2. QTc Stopping Criteria

A participant that meets the bulleted criterion below will be withdrawn from the study.

- QTc > 500 msec
- QTc increase from baseline > 60 msec
- The same QT correction formula must be used for each individual participant to determine eligibility for and discontinuation from the study. This formula may not be changed or substituted once the participant has been enrolled.
- For example, if a participant is eligible for the protocol based on QTcB, then QTcB must be used for discontinuation of this individual participant as well.
- Once the QT correction formula has been chosen for a participant's eligibility, the same formula must continue to be used for that participant for all QTc data being collected for data analysis. Safety ECGs and other non-protocol specified ECGs are an exception.

- The QTc should be based on the average of triplicate QTc values ECG readings obtained over a brief (e.g., 5-10 minute) recording period.

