## 1.3.2. CAB LA + RPV LA Injection Phase and Follow- up

Procedures	Injection Phase							Follow-up								
	Week 52	Week 36	Week 24	Week 12	Week 8	Day 28 (Week 4)	Day 22	Day 17	Day 15	Day 10	Day 7/8	Day 5	Day 4	Day 2	2h	1h
Permitted window for PK collection																
Interim Medical/Medication/ Drug / Alcohol History 	X															
Pregnancy Test	X															
12-Lead ECG 	X															
HIV Test	X															
Hematology; Clinical Chemistry	X															
Vital Signs 	X															
Administer CAB LA + RPV LA 	X															
CCI						X 	X 	X 	X 							
Injection site reaction assessment						X	X	X	X	X	X	X	X	X	X	X
AE Assessment 						X	X	X	X	X	X	X	X	X	X	X
Concomitant Medication Review	X	X	X	X	X	X	X	X	X	X	X	X	X	X	X	X
Blood plasma PK Sampling 	X	X	X	X	X	X	X	X	X	X	X	X	X	X	X	X

1. Participants who terminate before week 52 will be asked to return to the site for a withdrawal visit.

2. On Day 1, study personnel must verify the following pre-dose assessments to be within normal limits prior to injection: ECG, vital signs, pregnancy test (negative; FRP only), review AE assessment, and concomitant medications. If a clinical abnormality, clinically significant AE, or prohibited medication that precludes injection is observed/recordered, the medical monitor must be contacted for further instruction.
3. Participants will be asked to describe the comfort level with the injections received. **CCI**  
[REDACTED]
4. AE assessment will include a brief, symptom-directed physical exam as needed.
5. Total of 34 PK samples (17 each for CAB and RPV) will be collected through CAB LA + RPV LA Injection Phase and Follow-up.

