Inadvertent Intravenous Injection (Accidental Maladministration)	
As with any intramuscular injection, it is possible that CAB LA and/or RPV LA can be inadvertently administered intravenously instead of intramuscularly possibly resulting in higher than expected concentrations of CAB and/or RPV shortly after injection and lower concentrations thereafter. This could be due to administrator error, improper injection technique and / or improper needle length used based on body type.
	
 
Training will be provided to all sites on proper injection technique.
 
Should IM maladministration be suspected at any time (e.g., suspected under or overdose or inadvertent intravenous [IV] dosing), post dose ECG monitoring and vital signs or any other supportive testing may be obtained at the discretion of the investigator, and the medical monitor notified.
 
2-hour post dose PK samples will be for determination of CAB and RPV concentration and possible pharmacokinetic correlation with safety parameters such as ECG changes.
 

Hypersensitivity Reactions (HSR)	
Hypersensitivity reactions have been reported as uncommon occurrences with integrase inhibitors (INI), including the closely related compound dolutegravir, and were characterized by rash, constitutional findings, and sometimes, organ dysfunction, including liver injury.
 
While there have been no clinical cases of hypersensitivity to CAB to date, there is a theoretical risk of systemic or severe hypersensitivity reactions with or without hepatic symptoms associated with use of IM CAB. The long exposures anticipated after IM CAB injection may complicate the management of a drug hypersensitivity reaction, were it to occur.
	
 
The risk of developing a hypersensitivity reaction post administration of CAB and RPV will be minimized by the use of a 4-week oral lead-in of oral CAB/RPV to determine individual safety and tolerability prior to the introduction of IM CAB.
 
Clinical assessments, laboratory tests (including liver transaminases) and vital signs will be performed throughout this study. Results from these assessments may aid early detection of HSR.
 
Oral CAB will be withdrawn immediately for cases with suspected HSR during the oral CAB/RPV lead-in phase and participants would not proceed to the injection phase. Any HSR reactions that occur would be managed supportively.
 

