#### **4.1.4. Follow-up/Withdrawal Visit**

Because of the long acting PK profile of CAB LA + RPV LA, every effort should be made to bring participants back in through the 52 weeks post injections. Participants, who received CAB LA + RPV LA IM injection, will return to clinic for safety and PK assessments at Weeks 8, 12, 24, 36, and 52 post IM injections.

If a participant is withdrawn:

- prior to receiving the IM injection, then a follow-up/withdrawal visit should be scheduled 10-14 days after the last oral dose of CAB + RPV.
- after receiving IM dose of CAB LA and/or RPV LA injections, every effort should be made to bring the participants back in for the 52 weeks of safety and PK assessments following the injection(s), because of the long acting PK profile of CAB and RPV.

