# **7. DISCONTINUATION OF STUDY INTERVENTION AND PARTICIPANT DISCONTINUATION/WITHDRAWAL**

## **7.1. Discontinuation of Study Intervention**

Participants may voluntarily withdraw from the study at any time and for any reason. Site investigators and study staff may withdraw participants before their scheduled termination visit for safety, behavioral, or administrative reasons, or if the participants are unable or unwilling to comply with study procedures. The reasons for withdrawals will be recorded in the participants' study records. If a participant withdraws from the study, he/she may request destruction of any samples taken, and the investigator must document this in the site study records.

During the oral lead-in period, early withdrawal on medical grounds will occur if the participant develops a Grade 3 or higher AE that is judged by the investigator to be related directly to the study product (see [Appendix 3](#) and [Appendix 4](#) for definitions and grading of severity of adverse events), or a participant develops a grade 3 or higher clinical significant laboratory abnormality (see Division of AIDS [DAIDS] table [Appendix 7](#) for grading) or any AE that is deemed clinically significant by the investigator and is judged by the investigator to be related directly to the study product.

For liver-related stopping criteria, please refer to Section [7.1.1](#).

If a participant receives the injections, they will be followed 52-weeks post the final injection per protocol for appropriate procedures, including blood plasma PK sampling, and safety evaluations, and will not be removed from the study for medical reasons, unless they refuse to continue participation.

[figure not shown]
During the oral lead in phase additional pre-specified reasons for discontinuing a participant from the study (or, at minimum, discontinuing administration of study product and continuing safety evaluations) include:

- Pregnancy (please see Section 8.2.5)
- Protocol deviation
- Non-compliance
- Participant withdraws consent
- Participant lost to follow-up
- Investigator discretion
- Sponsor discontinues study

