## **7.2. Participant Discontinuation/Withdrawal from the Study**

- A participant may withdraw from the study at any time at his/her own request or may be withdrawn at any time at the discretion of the investigator for safety, behavioral, compliance or administrative reasons. This is expected to be uncommon.
- At the time of discontinuing from the study, if possible, an early withdrawal visit should be conducted. See SoA for data to be collected at the time of study discontinuation and follow-up and for any further evaluations that need to be completed.
- The participant will be permanently discontinued both from the study intervention and from the study at that time.
- If the participant withdraws consent for disclosure of future information, the sponsor may retain and continue to use any data collected before such a withdrawal of consent.
- If a participant withdraws from the study, he/she may request destruction of any samples taken and not tested, and the investigator must document this in the site study records.

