**Table 9 Assessment Windows for Injection & Follow-up Phase Data**

Parameter a	Analysis Window	Target Period Day	Analysis Timepoint
Assessments assigned to Phase=Injection (per Table 3)			
PK, Vital Signs, Labs, ECG, CCI	Injection Phase Day = 1	1	Day 1
PK, Vital Signs, CCI	Injection Phase Day = 2	2	Day 2
PK	Injection Phase Day = 4	4	Day 4
CCI	3 ≤ Injection Phase Day ≤ 4	4	Day 4
PK	Injection Phase Day = 5	5	Day 5
Vital Signs	3 ≤ Injection Phase Day ≤ 6	5	Day 5
CCI	5 ≤ Injection Phase Day ≤ 6	5	Day 5
ECG	2 ≤ Injection Phase Day	5	Day 5

Parameter a	Analysis Window	Target Period Day	Analysis Timepoint
PK	Injection Phase Day = 7	7	Day 7
PK	Injection Phase Day = 8	8	Day 8
CCI	7 ≤ Injection Phase Day	8	Day 8
Vital Signs	7 ≤ Injection Phase Day ≤ 9	8	Day 8
Labs	2 ≤ Injection Phase Day ≤ 10	8	Day 8
PK	Injection Phase Day = 10	10	Day 10
Vitals	10 ≤ Injection Phase Day ≤ 12	10	Day 10
PK	Injection Phase Day = 15	14	Day 15
Vital Signs	12 ≤ Injection Phase Day ≤ 16	14	Day 15
PK	Injection Phase Day = 17	17	Day 17
Vital Signs	17 ≤ Injection Phase Day ≤ 19	17	Day 17
Labs	11 ≤ Injection Phase Day ≤ 23	17	Day 17
PK	Injection Phase Day = 22	22	Day 22
Vital Signs	20 ≤ Injection Phase Day ≤ 25	22	Day 22
PK	Injection Phase Day = 28	28	Week 4
Vital Signs	26 ≤ Injection Phase Day	28	Week 4
Labs	24 ≤ Injection Phase Day	28	Week 4
	If none of the above		Day X, where X=Injection Phase Day
Assessments assigned to Phase=Follow-up (per Table 3)			
Vital Signs, Labs	(Date of Nominal Follow-up Week 4 Visit – CAB + RPV Injection Date) +2 ≤ Injection Phase Day ≤ 70	56	Week 8
PK	53 ≤ Follow-up Period Day ≤ 59	56	Week 8
Vital Signs, Labs	71 ≤ Follow-up Period Day ≤ 126	84	Week 12
PK	81 ≤ Follow-up Period Day ≤ 87	84	Week 12
Vital Signs, Labs	127 ≤ Follow-up Period Day ≤ 210	168	Week 24
PK	165 ≤ Follow-up Period Day ≤ 171	168	Week 24
Vital Signs, Labs	211 ≤ Follow-up Period Day ≤ 308	252	Week 36
PK	249 ≤ Follow-up Period Day ≤ 255	252	Week 36
Vital Signs, Labs, ECG	309 ≤ Follow-up Period Day	364	Week 52
PK	361 ≤ Follow-up Period Day ≤ 367	364	Week 52
	If none of the above		Day X, where X=Follow-up Phase Day
NOTES:			

 
OLI Day, Injection Day, and Follow-up Day are defined in Section 11.5.1.
 
			

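### Protocol 7.1.2 orders withdrawal from the study for a QTc breach in any phase, which contradicts the rule in 7.1 that keeps injected participants in follow-up for 52 weeks

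*Protocol*

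**What the plan says.** Protocol 7.1.2 (QTc Stopping Criteria) applies to a QTc above 500 msec or an increase from baseline above 60 msec. The consequence is mandatory and has no phase limit: "A participant that meets the bulleted criterion below will be withdrawn from the study". Section 8.1.3 sends the reader to Section 7 for the QTc withdrawal criteria and adds no limit either.

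Protocol 7.1, the parent section, provides that a participant who has received the injections is followed for 52 weeks, with PK sampling and safety evaluations, and "will not be removed from the study for medical reasons, unless they refuse to continue participation".

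Three other places bear on what happens after a withdrawal:

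- Section 7.2: "The participant will be permanently discontinued both from the study intervention and from the study at that time".
- Section 4.1.4, for a participant withdrawn after the IM dose: "every effort should be made to bring the participants back in for the 52 weeks of safety and PK assessments".
- Section 1.3.2, footnote 1: "Participants who terminate before week 52 will be asked to return to the site for a withdrawal visit".

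ECGs can be recorded after injection. SAP Table 9 has an ECG window with target Injection Day 5 ("2 ≤ Injection Phase Day") and one with target Week 52 ("309 ≤ Follow-up Period Day"). In Protocol 2.3.1, the row on inadvertent intravenous injection adds that, if maladministration is suspected, "post dose ECG monitoring and vital signs or any other supportive testing may be obtained at the discretion of the investigator".

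**The concern.** A QTc breach is a medical reason. Before injection the two rules agree: oral dosing stops, no long-acting injection is given, and the participant leaves. After injection they give opposite instructions. Sections 6.5 and 8 allow no waivers, so a site departs from the protocol whichever rule it follows.

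After injection, withdrawal has no dosing benefit because no further dose is planned. What it can affect is observation. Protocol Table 2 predicts half-lives of 6.5 weeks (CAB) and 28.1 weeks (RPV), so drug is still being absorbed long after the injection visit. A site that reads 7.1.2 together with 7.2 could close out a participant after a cardiac signal while exposure continues. Any PK data lost in this way would be lost because of a safety event, so the missingness would not be random.

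**Working it through.** **Do the two rules conflict?**

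| | 7.1.2 | 7.1 |
|---|---|---|
| Who | Any participant meeting a QTc criterion | Participants who have received the injections |
| Instruction | Withdraw from the study | Follow for 52 weeks; no removal for medical reasons |
| Exception | None | Participant refuses to continue |

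The overlap is an injected participant who meets a QTc criterion and is willing to stay. For that participant the instructions are incompatible.

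**Can the overlap occur?** Yes. SAP Table 9 assigns ECGs to analysis visits after injection, and the risk table allows unscheduled post-dose ECGs.

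**How do neighbouring rules handle it?** Section 7.1.1 (liver chemistry) stops the study intervention and does not order withdrawal from the study. Section 7.1 ties early withdrawal for Grade 3 or higher related events to the oral lead-in. Section 11.4.3 separates the phases for pregnancy: no injection if it occurs in the lead-in, follow-up to 52 weeks if it occurs after injection. Only the QTc rule lacks this separation.

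**What could one case cost?** The plan gives no figure to reproduce: there is no QTc event rate, and Protocol 10.2 makes no sample size calculation. The inputs are the planned number of about 15 (10.2) and the gluteal-model medians in Protocol Table 2.

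- Share of participants: 1/15 = 6.7%.
- Time at Injection Day 5: SAP 11.5.1 counts the dose date as Day 1, so Day 5 is 4 days, or 96 h, after dosing.
- Minimum unobserved share, 1 − AUC(0–Wk4)/AUC(0–Wk52). AUC is cumulative, so the Week 4 share is a floor for an earlier exit.
  - CAB: 1 − 1216/3655 = 66.7%.
  - RPV: 1 − 28354/102380 = 72.3%.
- Closer bound for 96 h, using AUC(0–96h) ≤ Cmax × 96:

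| Cmax used | Drug | Cmax × 96 | Divided by median AUC(0–Wk52) | Unobserved |
|---|---|---|---|---|
| Median | CAB | 2.13 × 96 = 204.5 | 204.5/3655 = 5.6% | 94.4% |
| Median | RPV | 56.0 × 96 = 5376 | 5376/102380 = 5.3% | 94.7% |
| Upper 90% PI | CAB | 5.80 × 96 = 556.8 | 556.8/3655 = 15.2% | 84.8% |
| Upper 90% PI | RPV | 151 × 96 = 14496 | 14496/102380 = 14.2% | 85.8% |

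These are ratios of predicted medians (or of an upper limit to a median), so they indicate size and are not estimates for a given person. Predicted CAB tmax (median 8 days, 90% PI 5 to 15) lies beyond 4 days. For such a participant, terminal half-life, KALA and AUC(0–∞) could not be estimated.

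**The case against.** The strongest reply is that the protocol already protects follow-up. Section 4.1.4 addresses withdrawal after injection and asks sites to pursue the full 52 weeks of safety and PK assessments. Section 8.2 keeps the investigator responsible for adverse events that led to discontinuation. A clinically significant ECG abnormality is an adverse event under 11.3.1, and 8.2.3 requires serious events to be followed until resolved or stabilised. The intent in 7.1 and in the pregnancy text is also consistent. One can therefore read 7.1.2 as a general rule qualified by the paragraph on injected participants.

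Most of this stands, and it limits the consequence. It does not remove the conflict. Section 4.1.4 does not say whether 7.1 or 7.1.2 governs, and a site that lets the specific rule prevail over the general one would apply 7.1.2, the less protective reading.

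Some stronger readings are tempting but not supported:

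- A reader might infer that a QTc withdrawal after injection necessarily ends observation. Sections 4.1.4 and 8.2 say otherwise, so loss of data is a risk only.
- A reader might infer that 4.1.4 and footnote 1 of the schedule contradict each other. They are compatible: a site can try to retain the participant and hold a withdrawal visit if that fails. The discontinuation bullet in 7.2 follows one on withdrawal by request or at the investigator's discretion, and 7.1.2 does not cite it.
- A reader might take the Day 5 ECG as established. Table 9 is a visit-slotting table, and its ECG window has no upper limit within the Injection Phase. The target day suggests a Day 5 ECG but does not prove one. The ECG columns of the schedule were not legible in the text reviewed.
- A reader might extend the point to the rash row in 2.3.1. That is risk-table text about oral RPV, and the point is not made here.

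**Conclusion.** The rule is wrong as written. For participants who have been injected, 7.1.2 requires what 7.1 forbids. This is a conflict in a mandatory safety rule rather than a missing detail, and it should be corrected.

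The expected effect is small. No event rate is given, and footnote 2 of the injection schedule requires a normal ECG before dosing, so cases are probably rare. One case would be about 6.7% of the planned participants. The loss of at least about two thirds of predicted AUC (about 85% to 95% on the Cmax bound) is not an expected loss. It needs a breach around Day 5, a site that puts 7.1.2 above 7.1, and a participant who does not return despite 4.1.4. A later exit loses less, and a breach at the Week 52 ECG costs no PK data.

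The figures also assume that absorption from the thigh resembles the gluteal model, as 4.2.2 anticipates. For RPV, the loss of half-life and AUC(0–∞) should not be overstated: 52/28.1 is about 1.85 predicted half-lives, so these parameters are weakly supported even with full follow-up. The analysis is descriptive, so no test is affected.

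**What to change.** In Protocol 7.1.2, limit withdrawal from the study to participants who have not yet been injected: oral dosing stops and no long-acting injection is given. Add that a participant who meets a QTc criterion after injection remains in 52-week safety and PK follow-up under 7.1 and 4.1.4 unless consent is withdrawn. Put a cross-reference to this in 7.2.

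The cost is a short wording change and one cross-reference. No visits, samples, SAP text or displays change.

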## **7.2. Participant Discontinuation/Withdrawal from the Study**

- A participant may withdraw from the study at any time at his/her own request or may be withdrawn at any time at the discretion of the investigator for safety, behavioral, compliance or administrative reasons. This is expected to be uncommon.
- At the time of discontinuing from the study, if possible, an early withdrawal visit should be conducted. See SoA for data to be collected at the time of study discontinuation and follow-up and for any further evaluations that need to be completed.
- The participant will be permanently discontinued both from the study intervention and from the study at that time.
- If the participant withdraws consent for disclosure of future information, the sponsor may retain and continue to use any data collected before such a withdrawal of consent.
- If a participant withdraws from the study, he/she may request destruction of any samples taken and not tested, and the investigator must document this in the site study records.

## **7.3. Lost to Follow Up**

A participant will be considered lost to follow-up if he or she repeatedly fails to return for scheduled visits and is unable to be contacted by the study site.

The following actions must be taken if a participant fails to return to the clinic for a required study visit:

- The site must attempt to contact the participant and reschedule the missed visit as soon as possible and counsel the participant on the importance of maintaining the assigned visit schedule and ascertain whether or not the participant wishes to and/or should continue in the study.
- Before a participant is deemed lost to follow up, the investigator or designee must make every effort to regain contact with the participant (where possible, 3 telephone calls and, if necessary, a certified letter to the participant's last known mailing address or local equivalent methods). These contact attempts should be documented in the participant's medical record.
- Should the participant continue to be unreachable, he/she will be considered to have withdrawn from the study.

Discontinuation of specific sites or of the study as a whole are handled as part of [Appendix 1](#).

## 8. STUDY ASSESSMENTS AND PROCEDURES

- Study procedures and their timing are summarized in the SoA.

If these assessments are scheduled for the same nominal time, THEN the assessments should occur in the following order:

- 12-lead ECG
- vital signs
- blood draws.

Note: The timing of the assessments should allow the blood draw to occur at the exact nominal time

- Protocol waivers or exemptions are not allowed
- Safety concerns should be discussed with the sponsor immediately upon occurrence or awareness to determine if the participant should continue or discontinue study intervention.
- Adherence to the study design requirements, including those specified in the SoA, is essential and required for study conduct.
- All screening evaluations must be completed and reviewed to confirm that potential participants meet all eligibility criteria. The investigator will maintain a screening log to record details of all participants screened and to confirm eligibility or record reasons for screening failure, as applicable.
- Procedures conducted as part of the participant's routine clinical management (e.g., blood count) and obtained before signing of ICF may be utilized for screening or baseline purposes provided the procedure met the protocol-specified criteria and was performed within the time frame defined in the SoA.
  - The maximum amount of blood collected from each participant over the duration of the study, including any extra assessments that may be required, will not exceed 500 mL.
  - Repeat or unscheduled samples may be taken for safety reasons or for technical issues with the samples.

### 8.1. Safety Assessments

Planned time points for all safety assessments are provided in the SoA.

#### 8.1.1. Physical Examinations

- A complete physical examination will include, at a minimum, assessments of the skin, cardiovascular, respiratory, gastrointestinal and neurological systems. Height and weight will also be measured and recorded.
- A brief physical examination will include, at a minimum, assessments of the skin, lungs, cardiovascular system, and abdomen (liver and spleen).

- Investigators should pay special attention to clinical signs related to previous serious illnesses.

